#### 7.4 Protocol Violation

Protocol deviations will be summarized by deviation category and treatment group. This analysis will be performed for all randomized patients.

#### 7.5 Data Handling

#### 7.5.1 Imputation of Missing data

Imputation for missing values are not applicable.

#### 7.6 Sample Size Calculation

120 male and female adults with probable or definitive Meniere's disease. This Phase 2b study (SPI-1005-251), is adequately powered to demonstrate a 50% improvement in a symptom of MD using the responder analysis detailed in below with 40 study participants per treatment group.

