of treatment, and 28 days after treatment. Hearing thresholds (HL) will be determined using puretone audiometric (air conduction) testing at 250, 500, 1000, 2000, 3000, 4000, 6000, and 8000 Hz, bilaterally. In addition, bone conduction testing with masking will be conducted if the air conduction threshold is >15 dBHL at 250, 500, 1000, 2000, or 4000 Hz. Bone conduction testing will only be performed at screening and in the affected ear (>15 dBHL). A word recognition test using the Wordsin-Noise Test (WINT) at 24, 20, 16, 12, 8, 4, and 0 Signal-to-Noise ratio (SNR) will be used to evaluate hearing.

Following completion of informed consent process and baseline assessments, the study participants will be evaluated by the investigator for enrollment eligibility. Participants that meet enrollment criteria will be randomized and assigned a Subject Identification Code from the list of Subject Identification Codes. The Subject Identification Code must be carefully matched to the study drug before the study drug is dispensed at Clinic Visits 1, and 2.

A general diagram of the study design is provided in Figure 1.

This document is confidential and proprietary to Sponsor and EA and for restricted circulation and access only. No part of it may be transmitted, reproduced, published or used by any person/s without prior written authorization.

Version No.: Final 1.0

Page 11 of 38

A ECRON ACUNOVA

Sponsor Study No: SPI-1005-251

Sponsor Name: Sound Pharmaceuticals, Inc.

NLS Study Code: SPI-1005-251 Short Title of Study: SPI-1005-251 (Sound Pharmaceuticals, Inc) Screen for Screen participants (n=168 estimate) by inclusion and exclusion criteria Eligibility including history and review of systems Estimated Excluded (n=48) Did not meet I/E criteria (n=25) Declined to participate (n=13) Other reasons (n=10) Clinic Visit 1 Informed consent process, perform baseline assessments, confirm Day -28 to 1 eligibility, randomize, complete enrollment by providing study drug. Clinic Visit 2 Day 14 Perform protocol required assessments. Day 28 Clinic Visit 3 Perform protocol required assessments. Day 56 Clinic Visit 4 Final Assessments

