#### 7.3.2 Intent-to-Treat (ITT) Analysis Population

The ITT Efficacy Analysis population includes all patients from the randomized population who have received at least one dose of study drug and who have an evaluated post baseline efficacy assessment. The efficacy assessments include the evaluation of:

- Non- missing Pure-tone audiometry at Visit 3 or Visit 4
- Non- missing Words-in-Noise Test at Visit 3 or Visit 4
- Non-missing Tinnitus Functional Index (TFI) at Visit 2 or Visit 3 or Visit 4
- Non-missing Tinnitus Loudness (TL) at Visit 2 or Visit 3 or Visit 4
- Non-missing Vertigo Symptom Scale (VSS) at Visit 2 or Visit 3 or Visit 4

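### The SAP's power claim for 40 per group does not define its 50% improvement: power runs from 18% to over 99% depending on the reading, and no losses are allowed for

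*SAP*

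**What the plan says.** SAP 7.6 sets the size at "120 male and female adults with probable or definitive Meniere's disease", "with 40 study participants per treatment group", and says that the study "is adequately powered to demonstrate a 50% improvement in a symptom of MD using the responder analysis detailed in below". The section contains nothing else.

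Other parts of the SAP bear on it:

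- **7.1** sets all tests two-sided at 0.05 unless stated otherwise.
- **8.3.1.1 to 8.3.1.5** give the responder cut-offs and a chi-square or Fisher's exact test for each of five measures. They give no expected response rates and no power.
- **6.1, Figure 1** starts from "Screen participants (n=168 estimate) by inclusion and exclusion criteria" and subtracts 48 who leave before randomisation.
- **7.3.2** limits the ITT set to randomised patients "who have received at least one dose of study drug and who have an evaluated post baseline efficacy assessment".
- **7.3.4** limits the Per-Protocol set further, by Visit 3 efficacy data, capsule compliance, eligibility, baseline WINT score and other major deviations.
- **7.5.1** rules out imputation, and **8.3.1** makes both sets primary.

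**The concern.** A power statement tells the reader which effects a non-significant result would count against. This one cannot do that, because a 50% improvement in a responder analysis can mean at least four things:

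- a responder rate 1.5 times placebo;
- 50% of drug patients responding;
- a 50-point difference;
- a halving of non-response.

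These differ several-fold in the sample they need. Someone who takes the first meaning and sees a null result would wrongly conclude that a 1.5-fold effect had been tested with good power.

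The 40 per group is also the number randomised, whereas the analyses use the number evaluable.

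**Working it through.** **Inputs from the documents.** n = 40 per arm (SAP 7.6); two-sided α = 0.05 (SAP 7.1); 1:1:1 allocation (SAP 7.2); chi-square or Fisher's exact test (SAP 8.3.1.1 to 8.3.1.5).

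**Assumptions, because the documents give no value.** Placebo response of 20% to 50%; one dose against placebo; one endpoint; loss of 15% (range 5% to 20%).

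**The plan's own figure.** The 40 per group cannot be reproduced, since there is no power target and no pair of response rates to put into a formula.

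**Method.** The main figures are exact: sum the binomial probabilities of every pair of responder counts for which the uncorrected chi-square test gives p ≤ 0.05. The normal approximation serves as a check:

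power = Φ{ [ |p₁ − p₀| − 1.96·√(2p̄(1 − p̄)/n) ] / √([p₀(1 − p₀) + p₁(1 − p₁)]/n) }, with p̄ = (p₀ + p₁)/2.

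For 30% v 45% with n = 40, p̄ = 0.375. The first root times 1.96 is 0.2122 and the denominator is 0.1069. So power = Φ[(0.15 − 0.2122)/0.1069] = Φ(−0.58) = 28%. Exact enumeration gives 28.5%.

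**Reading 1: responder rate 1.5 times placebo, 40 per arm**

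| Placebo v drug | Exact chi-square | Normal check | Fisher's exact | n per arm for 80% |
|---|---|---|---|---|
| 20% v 30% | 17.7% | 17.5% | 12.3% | 294 |
| 30% v 45% | 28.5% | 28.1% | 21.2% | 163 |
| 40% v 60% | 45.8% | 43.1% | 36.9% | 97 |
| 50% v 75% | 64.7% | 64.1% | 55.9% | 58 |

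Power reaches 80% at a placebo rate of about 56%. Splitting α over two doses (0.025 each) lowers the exact range to about 11% to 55%. Pooling the doses (80 v 40, normal formula) raises it to 20% to 78%.

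**Other readings, 40 per arm, exact**

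- 50% responding on drug: 82%, 65% and 46% power at placebo 20%, 25% and 30%.
- 50-point difference: at least 99.8% at placebo 10% to 50%.
- Non-response halved: 97%, 90%, 80% and 65% at placebo 20%, 30%, 40% and 50%.

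**Drug response detectable with 80% power (exact chi-square)**

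| Placebo | 40 per arm | Difference | 34 per arm | Difference |
|---|---|---|---|---|
| 20% | 49.4% | 29.4 points | 51.4% | 31.4 points |
| 30% | 60.2% | 30.2 points | 63.8% | 33.8 points |
| 40% | 70.2% | 30.2 points | 73.2% | 33.2 points |
| 50% | 79.5% | 29.5 points | 81.1% | 31.1 points |

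**Losses.** 25 + 13 + 10 = 48, and 168 − 48 = 120 = 3 × 40. The 48 are excluded before randomisation, so nothing is held back for losses afterwards. A 15% loss leaves 40 × 0.85 = 34 per arm. On the normal formula, power for 30% v 45% falls from 28.1% at 40 per arm to 26.9%, 25.7%, 24.5% and 23.3% at losses of 5%, 10%, 15% and 20%.

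**The case against.** The strongest reply is that the SAP never says 1.5-fold. A reader might infer from the 18% to 65% range that the trial is underpowered for its stated aim. The documents do not support that. The figures rest on one reading and on a placebo range that they do not give. On a 50-point difference, or 50% v 20%, 40 per arm is enough. Nor do the documents rule out placebo rates above 56%: the audiometry criterion is met by 10 dB at any one of three frequencies, in a disease whose entry criteria include fluctuating hearing loss. This part of the reply stands.

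Three other strong readings also fail:

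- That only a 50-point difference is well powered. About 30 points is enough.
- That α is missing. SAP 7.1 supplies it.
- That losses undermine the design. They move the detectable difference by only about 2 to 4 points, and a 50-point difference keeps at least 99% power at 34 per arm.

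Two limits remain. Only the protocol synopsis and schedule were available, and some SAP text near 8.3.1 was removed, so a fuller rationale may exist elsewhere. The power figures also apply only to the responder tests, not to the repeated-measures models that the SAP plans for the continuous outcomes.

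None of this makes the sentence in 7.6 checkable. A claim whose power runs from 18% to over 99% according to how it is read still needs a definition.

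**Conclusion.** The point holds as a defect in a stated design property, of moderate weight. The words "is adequately powered to demonstrate" a 50% improvement are true for some meanings of that phrase and false for others, and 7.6 does not say which is meant. What the design supports is 80% power for a difference of about 29 to 30 points, given 40 evaluable per arm, a two-sided 5% chi-square test, one dose, one endpoint and placebo rates of 20% to 50%. Fisher's exact test or adjustment for two doses lowers the power.

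Separately, 40 is the analysed size only if nobody is lost, while both primary sets exclude randomised patients and nothing is imputed. The size of that effect depends on an assumed loss rate and is modest. No planned estimate, test or population is affected.

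**What to change.** Replace the unqualified sentence in SAP 7.6 with:

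> With 40 evaluable participants per arm and a two-sided 5% chi-square test of one dose against placebo on a single responder endpoint, power is 80% for a difference of about 30 percentage points (for example 30% v 60%). With 34 evaluable per arm (15% loss, assumed) the detectable difference is about 31 to 34 points. Power is lower with Fisher's exact test or with adjustment for two doses.

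If the sponsor had particular placebo and active rates in mind, state them, with the endpoint and the resulting power. If not, drop the claim of adequate power for a 50% improvement.

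The cost is SAP wording only, and the stated figure becomes less favourable. Do not enrol more: the final SAP is dated 30 May 2019, and 8.6 already describes site participation in the past tense.

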#### 7.7 Interim Analysis

There is no interim analysis planned for this study.

This document is confidential and proprietary to Sponsor and EA and for restricted circulation and access only. No part of it may be transmitted, reproduced, published or used by any person/s without prior written authorization.

Version No.: Final 1.0

ECRON ACUNOVA

Sponsor Study No: SPI-1005-251

Sponsor Name: Sound Pharmaceuticals, Inc.

 NLS Study Code: SPI -1005 -251
 Short Title of Study: SPI -1005 -251 (Sound Pharmaceuticals, Inc)

Page 16 of 38

#### 7.8 Definitions and Derived Variables

For the statistical analysis, two different doses and placebo will be denoted according to the following table.

| Treatment             | Label           |
|-----------------------|-----------------|
| SPI-1005 po BID 200mg | SPI-1005 200 mg |
| SPI-1005 po BID 400mg | SPI-1005 400 mg |
| Placebo po BID        | Placebo         |

In the following table, the definitions and calculation of derived variables are summarised.

| Variable / Term | Definition / Way of calculation   |  |
|-----------------|---|--|
| Baseline        | The last assessment on or before to the treatment start date. The most recent measurement prior to treatment start regardless of whether the measurement is collected at a scheduled or unscheduled visit will be considered for the baseline.  |  |
| End of study    | The date on which the last patient completes the last visit (includes follow-
up visit).   |  |
| BMI             | Weight in kg / Height in m    |  |
| Treatment Start | 
 
The earliest date of 'date of drug dispense' (Date of dispensing) from Study
 
Drug Dispensing and Drug Accountability eCRF form, where the patient has:
 
Answered 'Yes' to question, Study medication dispensed? And,
 
Recorded at least one capsule used for the question, 'Number of capsules taken'
 
If the drug administration date is unavailable and only the last dose date of the patient is available, then the Randomization date will be considered as the treatment start date.
 
 |  |

#### **Confidentiality Statement**

A ECRON ACUNOVA

Sponsor Study No: SPI-1005-251

Version No.: Final 1.0

NLS Study Code: SPI-1005-251

Page 17 of 38

Sponsor Name: Sound Pharmaceuticals, Inc.

Short Title of Study: SPI -1005 -251 (Sound Pharmaceuticals, Inc)

| Variable / Term                 | Definition / Way of calculation  |  |
|---------------------------------|--|--|
|                                 | The treatment end date is taken from the field:  |  |
|                                 | 'Date of last study medication taken' from 'Study Completion or Early  |  |
|                                 | Termination' page.   |  |
| Treatment End                   | If the 'Date of last study medication taken' is missing and there is evidence  |  |
|                                 | that the patient has taken the study medication, the last visit date will be   |  |
|                                 | considered as 'Treatment end date'.  |  |
|                                 | An adverse event (AE) will be considered as treatment-emergent if the time   |  |
| Treatment Emergent
AE (TEAE) | of onset is on or after the time of the first randomized study drug  |  |
|                                 | administration (treatment start date).   |  |
| Duration of exposure            | ration of Treatment end date - treatment start date + 1, refer to section 8.2.1 in S for details                     |  |
| Treatment
compliance         | (Total number of capsules used/Total number of capsules to be taken) *100, refer to section 8.2.2 in SAP for details |  |
| Geo CV%                         | sqrt(exp(log SD)-1)*100  |  |

#### 7.9 Statistical Software

All statistical analyses will be performed with SAS®, Version 9.2 or higher on a MS-Windows platform.

## **8** STATISTICAL ANALYSES

#### 8.1.1 Subject Disposition

The number of patients who have completed the study or early termination from the study and reasons for discontinuations will be grouped by treatment. The summary of patient disposition will be tabulated for all randomized, safety, ITT and PK analysis populations.

#### 8.1.2 Inclusion/Exclusion Criteria

The number and percentage of patients violating each inclusion/exclusion criterion will be presented by criterion. Violation of inclusion/exclusion criteria will be listed.

This document is confidential and proprietary to Sponsor and EA and for restricted circulation and access only. No part of it may be transmitted, reproduced, published or used by any person/s without prior written authorization.

Version No.: Final 1.0

ECRON ACUNOVA

Sponsor Study No: SPI-1005-251

Sponsor Name: Sound Pharmaceuticals, Inc.

| NLS Study Code: SPI-1005-251 S | Short Title of Study: SPI-1005-251 (Sound Pharmaceuticals, Inc) |
|--------------------------------|---|

Page 18 of 38

#### 8.1.3 Demographic Data and Baseline Characteristics

Demographic characteristics include age, gender, ethnicity. Baseline characteristics include height, weight, BMI, TFI, VSS, PTA and WINT.

Frequency and percentage will be presented for gender, ethnicity. Descriptive statistics will be presented for age (years), height (cm), weight (Kg), BMI (kg/m^2). These analyses will be performed for the Randomized, Safety, ITT and Per-Protocol populations.

Demographic and baseline characteristics will be presented in the by-patient listings. A data listing will be produced for the randomization details.

#### 8.1.4 Medical History

Medical history terms will be coded using MedDRA dictionary version 19.1.

Medical history will be summarized by MedDRA system organ class and preferred term for safety population. All medical history will be listed by patient and treatment group.

#### 8.1.5 Prior and Concomitant Medication

Prior and concomitant medications will be assessed at screening and at each subsequent study visit. Medications will be coded using WHO Drug Dictionary version MAR2017.

Medication will be classified as prior, if the end date is known and is before the first use of the study medication. Medications that are ongoing or ended after the first use of the study medication will be classified as concomitant. If the end date of the medication is unknown, it will also be considered concomitant. If the end date is partially known, the medication will be considered concomitant, unless the known part of the end date rules out the possibility that the medication could have ended before the start of the study drug.

Prior and concomitant medications will be separately summarized by ATC class (the highest available level) and preferred name for the safety population. The prior and concomitant medications will be listed in a by-patient listing.

This document is confidential and proprietary to Sponsor and EA and for restricted circulation and access only. No part of it may be transmitted, reproduced, published or used by any person/s without prior written authorization.

Version No.: Final 1.0

ECRON ACUNOVA

Sponsor Study No: SPI-1005-251

Sponsor Name: Sound Pharmaceuticals, Inc.

NLS Study Code: SPI -1005 -251

Short Title of Study: SPI-1005-251 (Sound Pharmaceuticals, Inc)

#### 8.2 Extent of Exposure and Compliance

#### 8.2.1 Treatment Exposure

Treatments will be dispensed at baseline to patients based on the randomized group assignments and the patients will receive the treatment for a duration of 28 days.

The earliest date of 'date of drug dispense' (Date of dispensing) from Study Drug Dispensing and Drug Accountability eCRF form, where the patient has:

• Answered 'Yes' to question, 'Study medication dispensed?' and,

Page 19 of 38

• Recorded at least one capsule used for the question, 'Number of capsules taken'

If the drug administration date is unavailable and the last dose date of the patient is only available, then the Randomization date will be considered as treatment start date.

The treatment end date is taken from the field:

- 'Date of last study medication taken' from 'Study Completion or Early Termination' page. If the date of last study drug administration is missing and there is evidence that the patient has taken study medication, last visit date will be considered as 'Treatment end date'.
- Duration of treatment exposure is derived as treatment end date treatment start date + 1

The duration of treatment exposure will be summarized descriptively by treatment group for safety population. Data listing will be presented for study drug administration.

#### 8.2.2 Treatment Compliance

Treatment compliance is defined as intake of 80% to 120% of the dispensed capsules by an individual patient during the treatment period. Hence the compliance is computed as:

• (Total number of capsules used/Total number of capsules to be taken) \*100

Where the total number of capsules used is derived as the sum of results recorded for the question 'Number of capsules taken' in the drug accountability form.

Data listing also will be presented for treatment compliance.

#### 8.3 Efficacy Analysis

#### 8.3.1 Analysis of Primary Endpoint

Primary analyses will use the Per-Protocol analysis population and Intent-To-Treat analysis population.

#### 8.3.1.1 Pure-Tone Audiometry

Pure-tone audiometry (PTA) will be measured at visit 1, visit 3 and visit 4.

Both the actual ear value and calculated change from baseline PTA data will be summarized by visits and treatment groups.

PTA data will be analyzed with a mixed-effects model for repeated measures, and a post-hoc Bonferroni correction analysis with significance set to 0.05. The calculated change of PTA data will be calculated by the difference of the actual ear value at baseline and the actual ear value at each visit post baseline. The primary assessment of PTA data will consider a  $\geq 10$  dBHL improvement from baseline as a clinically relevant response (only low frequency: 250, 500, 1000 Hz). The secondary assessments of PTA data will consider an improvement from baseline of  $\geq 10$  dBHL at two adjacent frequencies or  $\geq 20$  dBHL at one frequency as clinically relevant responses (only low frequency: 250, 500, 1000 Hz). The final processed data will be analyzed using a chi-square test or Fisher's Exact test to assess the improvement between treatment groups.

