#### 8.3.1.2 Words-in-Noise Test

The Words-in-Noise Test (WINT) will be measured at visit 1, visit 3 and visit 4.

Both the actual ear value and calculated change from baseline WINT data will be summarized by visits and treatment groups.

WINT data will be analyzed with a mixed-effects model for repeated measures, and a post-hoc Bonferroni correction analysis with significance set to 0.05. The calculated change of WINT data will be calculated by the difference of the actual ear value at baseline and the actual ear result at each visit post baseline. The primary assessment of WINT data will consider a  $\geq 10\%$  improvement from baseline as a clinically relevant response. The secondary assessments of WINT data will consider an improvement from baseline of  $\geq 20\%$  or  $\geq 4$  words as clinically relevant responses. The final processed data will be analyzed using a chi-square test or Fisher's Exact test to assess the improvement between treatment groups.

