The TFI data will be analyzed with a mixed-effects model for repeated measures, and a post-hoc Bonferroni correction analysis with significance set to 0.05. The calculated change of TFI data will be calculated as the difference of the PRO value at baseline and the PRO value at each post baseline timepoint. The improvement will be considered only if the difference between post baseline and baseline value is  $\geq 10$  pts. The final processed data will be analyzed using a chi-square test or Fisher's Exact test to assess the improvement between treatment groups.

This document is confidential and proprietary to Sponsor and EA and for restricted circulation and access only. No part of it may be transmitted, reproduced, published or used by any person/s without prior written authorization.

Statistical Analysis Plan Version No.: Final 1.0

Page 22 of 38

Sponsor Study No: SPI-1005-251 Sponsor Name: Sound Pharmaceuticals, Inc.

CRON ACUNOVA

NLS Study Code: SPI -1005 -251

Short Title of Study: SPI-1005-251 (Sound Pharmaceuticals, Inc)

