#### 8.3.1.4 Tinnitus Loudness

Tinnitus loudness (TL) will be measured at visit 1, visit 2, visit 3 and visit 4. TL is assessed from question number two of the TFI.

The actual patient reported outcome (PRO) value and change from baseline for TL will be summarized by visits and treatment groups. TL data will be analyzed with a mixed-effects model for repeated measures, and a post-hoc Bonferroni correction analysis with significance set to 0.05. The calculated change of TL data will be calculated as the difference of the PRO value at baseline and the PRO value at each post baseline timepoint. The improvement will be considered only if the difference between post baseline and baseline value is  $\geq 2$  pts. The final processed data will be analyzed using a chi-square test or Fisher's Exact test to assess the improvement between treatment groups.

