#### 8.3.1.5 Vertigo Symptom Scale

Vertigo Symptom Scale (VSS) will be measured at visit 1, visit 2, visit 3 and visit 4.

The actual patient reported outcome (PRO) value and change from baseline for VSS will be summarized by visits and treatment groups.

VSS will be analyzed for Total Scale, Vertigo/balance sub-scale and Autonomic/anxiety sub-scale. The Vertigo/balance sub-scale will be calculated as the sum of questions 1, 3, 4, 6, 8, 10, 13 and 15. The Autonomic/anxiety sub-scale will be calculated as the sum of questions 2, 5, 7, 9, 11, 12 and 14. The range for the Vertigo/balance sub-scale will be 0 - 32 and the range for Autonomic/anxiety sub-scale will be 0 - 32.

VSS data will be analyzed with a mixed-effects model for repeated measures, and a post-hoc Bonferroni correction analysis with significance set to 0.05.

The calculated change of VSS data will be calculated as the difference of the PRO value at baseline and the PRO value at each post baseline timepoint. The improvement will be considered only if the difference between post baseline and baseline value is  $\geq 6$  pts. The final processed data will be analyzed using a chi-square test or Fisher's Exact test to assess the improvement between treatment groups.

This document is confidential and proprietary to Sponsor and EA and for restricted circulation and access only. No part of it may be transmitted, reproduced, published or used by any person/s without prior written authorization.

Version No.: Final 1.0

ECRON ACUNOVA Sponsor Study No: SPI-1005-251 Sponsor Name: Sound Pharmaceuticals, Inc.

NLS Study Code: SPI-1005-251

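### The SAP specifies no baseline covariate in the mixed models for PTA, WINT, TFI, TL and VSS, although each baseline is collected

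*SAP*

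**What the plan says.** SAP section 8.3.1 (Analysis of Primary Endpoint) describes the continuous analysis of each measure in one near-identical sentence:

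- 8.3.1.1: "PTA data will be analyzed with a mixed-effects model for repeated measures"
- 8.3.1.2: "WINT data will be analyzed with a mixed-effects model for repeated measures"
- 8.3.1.3: "The TFI data will be analyzed with a mixed-effects model for repeated measures"
- 8.3.1.4: "TL data will be analyzed with a mixed-effects model for repeated measures"
- 8.3.1.5: "VSS data will be analyzed with a mixed-effects model for repeated measures"

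Each sentence adds a post-hoc Bonferroni correction at 0.05. None lists fixed effects, covariates, a covariance structure or the response variable. Section 6.2 sends exact computations to section 7.8, which contains no model terms either.

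The baselines exist. Section 8.1.3 states "Baseline characteristics include height, weight, BMI, TFI, VSS, PTA and WINT". Tinnitus loudness comes with the TFI, because "TL is assessed from question number two of the TFI". Baseline is used to form change scores; for PTA, "The calculated change of PTA data will be calculated by the difference of the actual ear value at baseline" and the value at each later visit. The section 13 table list covers both actual values and changes for each measure, in the Intent-to-Treat and Per-Protocol populations. It does not settle which of the two the model takes as its response.

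**The concern.** A patient's starting value usually predicts the later value on scales such as these. A model that ignores it leaves explainable variation in the error term, and a chance difference in starting values between arms passes into the estimated effect.

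Three features make this relevant here. Entry requires at least 30 dBHL at one of three low frequencies (protocol synopsis), and selecting on a threshold invites regression to the mean on that measure. The inclusion criteria shown in the synopsis set no minimum TFI, loudness or VSS score, so some patients may start with little room to improve. The SAP itself treats baseline as influential for WINT: section 7.3.4 removes patients with an unusually high baseline score from the Per-Protocol population, yet 8.3.1.2 names no baseline term.

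At stake are the width of the intervals and the stability of the five continuous comparisons. So is the choice left open by the text: with or without baseline, actual value or change, decided after the data are seen.

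**Working it through.** **Inputs from the documents.** 40 patients per group (SAP 7.6), 1:1:1 allocation (7.2), two-sided tests at 0.05 (7.1). The figure of 40 is justified by a responder analysis, with no control rate, power value or standard deviation, so it cannot be reproduced and says nothing about the precision of the continuous models.

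**Assumptions, not in the documents.** Equal variance at baseline and follow-up (SD = 1), one follow-up visit, and baseline-to-post correlation r from 0.5 to 0.8.

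**Step 1: per-patient variance under three models.**

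- Post-treatment value only: 1
- Change score: 2(1 − r)
- Baseline-adjusted: 1 − r²

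So adjusted / change = (1 − r²) / [2(1 − r)] = (1 + r)/2, and adjusted / post = 1 − r².

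| r | adjusted / change | saving | 40 ÷ ratio | adjusted / post | saving |
|---|---|---|---|---|---|
| 0.5 | 0.75 | 25% | 53 | 0.75 | 25% |
| 0.6 | 0.80 | 20% | 50 | 0.64 | 36% |
| 0.7 | 0.85 | 15% | 47 | 0.51 | 49% |
| 0.8 | 0.90 | 10% | 44 | 0.36 | 64% |

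The fourth column is the number per arm that an unadjusted change-score analysis would need to match 40 per arm with adjustment. Outside the range, at r = 0.9, the saving against a change score falls to 1 − 0.95 = 5%.

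**Step 2: what this means for power.** Take an assumed true difference of 0.5 SD and a single two-sided comparison at 0.05, with no multiplicity correction. The standard error is √(2v/40), where v is the variance from step 1.

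| r | post only | change | adjusted |
|---|---|---|---|
| 0.5 | 60.9% | 60.9% | 73.3% |
| 0.6 | 60.9% | 70.5% | 79.8% |
| 0.7 | 60.9% | 82.3% | 87.9% |
| 0.8 | 60.9% | 94.2% | 96.1% |

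**Step 3: chance imbalance.** The difference in baseline means between two arms of 40 has standard error √(2/40) = 0.224 SD, so 95% of randomisations fall within ±1.96 × 0.224 = ±0.44 SD. Given an imbalance of 0.44 SD, the unadjusted estimates move by:

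- post-value model: r × 0.44 = 0.22 SD (r = 0.5) to 0.35 SD (r = 0.8)
- change-score model: (r − 1) × 0.44 = −0.22 SD to −0.09 SD, that is, in the opposite direction

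These shifts average to zero over randomisations, and type I error is kept.

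**The case against.** The strongest reply is that silence is not exclusion. The five sections do not list treatment or visit either, and nobody would conclude that those are absent. The wording fits a model with a baseline covariate. It also fits one with Visit 1 as a repeated response; if the arms share a common baseline mean in that model, its precision is close to that of covariate adjustment. Any text between the opening of 8.3.1 and 8.3.1.1 was not available to check. All of this stands: a reader might infer that the SAP has decided against baseline adjustment, and the documents do not show that. What they show is that adjustment is not pre-specified.

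Three other stronger readings also fail.

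- **That the estimates are biased.** Under 1:1:1 randomisation both unadjusted contrasts are unbiased over randomisations. The shifts in step 3 are conditional on the imbalance that happens to occur.
- **That the primary efficacy tests are weakened.** The primary parameters in 6.2.1 are responder rates, compared by chi-square or Fisher's exact test. A covariate in the mixed model does not touch them. Nor do the documents give figures showing that the continuous analysis is the more powerful one.
- **That randomisation is unstratified, so imbalance is uncontrolled.** SAP 7.2 mentions only the allocation ratio, but the public protocol is a summary, and absence of stratification cannot be inferred from it.

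The size also depends wholly on an assumed correlation and on the response variable. With change scores and a high correlation the gain is small.

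The objection does not remove the point. The models sit under the primary-endpoint heading with their own tables in both populations, and a model run on the present wording without baseline is the less precise one.

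**Conclusion.** The concern holds as a gap in specification with a known cost. The visible SAP names no baseline covariate for any of the five mixed models, although all five baselines are collected. If the models are run without one, the variance of the treatment contrast is larger than it need be. Adjustment would remove 25% to 10% of it against a change-score model, or 25% to 64% against a raw post-value model. The estimates also remain exposed to chance baseline differences of up to about 0.44 SD. These figures assume equal variances, a single follow-up visit and a correlation of 0.5 to 0.8, none of which comes from the documents.

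This is a matter of precision and pre-specification in the continuous analyses. It is not a failure of validity, and it leaves the responder results as they are. The change should be made, but the trial's main efficacy comparison does not depend on it.

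**What to change.** Before unblinding, put text of this kind in SAP 8.3.1.1 to 8.3.1.5: *Change from baseline at the post-baseline visits will be modelled with treatment, visit, treatment-by-visit, the baseline value of the same measure and baseline-by-visit as fixed effects, with the correlation among a patient's repeated measurements modelled.* For PTA and WINT, add that the baseline is taken from the same ear as the outcome, and for PTA at the same frequency.

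With baseline and baseline-by-visit in the model, the treatment contrast is the same whether the response is the change or the actual value, so that open choice no longer matters.

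The cost is a few added terms in the model code and no new data. TFI, loudness and VSS need nothing further. PTA is measured in both ears at eight frequencies (SAP 6.1), so the ear and frequency entering the model must be defined first; WINT needs the ear defined. The SAP needs both definitions in any case. Which visit and which contrasts take priority is a separate question that this change leaves alone.
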